# 5.3 Fallzahlschätzung

A sample size of n = 62 (31 VWD cases and 31 controls) was required to detect an inter-group difference of 5.5% [4] GBI or BOP with a type 1 error  $\alpha$  < 0.05 and a test power of 80% (http://jumbo.uni-muenster.de/fileadmin/jumbo/applets/falla.html). After inclusion of 24 type 2 and 3 VWD cases no further type 2 and 3 VWD cases could be recruited at the Haemophilia Centre, Medical Clinic III/Institute for Transfusion medicine, Hospital of the Johann Wolfgang Goethe-University Frankfurt/Main. Thus, the study was analyses with 24 cases and 24 matched controls.

# 5.4 Study type

Prospective clinical case control study

# 5.5 Hematologic examinations

Twenty ml of blood was sampled from an arm vein. The following data were assessed at the Haemophilia Centre for clinical routine during VWD patient care and due to study design as well as to determine whether haemotological disease was present or not in the controls:

- von Willebrand parameters (VWF antigen [VWF:Ag], VWF activity [VWF:Act], coagulation factor VIII [FVIII:C])
- Current medication if any

Also diabetes mellitus and glycemic control may interfere with systemic as well as periodontal inflammation and, hence, gingival bleeding [14, 15]. Even so called prediabetes may contribute to inflammation. However, the state of prediabetes may not be known by the affected individual and not detected by medical history [15]. Thus, HbA1c as a measure for glycemic control was assessed also.

VWF:Ag and VWF:Act were measured turbidimetrically using a BCS (Siemens, Marburg, Germany). FVIII:C was assessed with specific agents on a coagulation analyzer (ACL-700®, IL Instrumentation Laboratory, Kirchheim, Germany).

[name] & [name] (143/15: Version 2: 27.05.2015)

# 5.6 Periodontal examinations

For all participants, a commercially available test (PerioSafe®, Dentagnostics, Jena, Germany) was performed to detect activated matrix metalloproteinase 8 (aMMP-8) from the gingival sulcus. First, patients rinsed with tap water for 30 seconds then spat the water out. After 1 minute, the patients rinsed with 5mL of purified water for 30 seconds and spat the sample back into the test cup. A syringe was used to gather 2mL of the sampled saliva and water mixture. A filter was then put onto the syringe and 3 drops of the saliva was pressed through the filter into the ELISA kit. After 5-10 minutes, the result was read from the test kit [16]. If both the control and test strips were visible ( $\geq$  25 ng aMMP 8 per mL), the respective test was positive.

The following clinical parameters were assessed at 6 sites per tooth (mesiobuccal, buccal, distobuccal, mesiolingual, lingual, distolingual) [4]:

- modified Gingival Bleeding Index (GBI) [17]
- modified Plaque Control Record (PCR) [18]
- PPD and recession to the nearest 0.2 mm using an electronic probe (Florida Probe, Version 3.2, Gainesville, FL, USA). Recession was assessed from the cemento-enamel junction (CEJ) to the gingival margin. At sites where the CEJ was destroyed by restorations the restoration margin (RM) was used as reference. At sites where the CEJ or RM was located apically from the gingival margin the value for recession was negative
- Bleeding on probing (BOP) recorded as positive when bleeding occurred within 30 seconds from probing. For each patient a BOP index was calculated providing the amount of sites with positive BOP in % per patient.
- Attachment loss was calculated as sum of PPD and recession. At sites where the gingival margin was located coronally of the CEJ recession was scored as a negative value.

All individuals were classified into the following diagnoses [14, 19]:

- plaque-induced gingivitis (PPD < 3.6 mm; PAL-V  $\leq$  2 mm),
- generalized mild, localized moderate chronic periodontitis (PPD ≥ 3.6 mm; PAL-V 3 to 4 mm ≤ 30% of sites; 1 to 2 mm > 30% of sites),
- generalized mild, localized severe chronic periodontitis (PPD ≥ 3.6 mm; PAL-V ≥ 5 mm ≤ 30% of sites; 1 to 2 mm > 30% of sites)
- generalized moderate chronic periodontitis (PPD ≥ 3.6 mm; PAL-V 3 to 4 mm > 30%)
- generalized moderate localized severe chronic periodontitis (PPD ≥ 3.6 mm; PAL-V 3 to 4 mm > 30%; ≥ 5 mm ≤ 30%)

In all individuals hematological and periodontal examinations were obtained within 24 hours. After dental and periodontal examination all patients received oral hygiene instructions and professional tooth cleaning. In cases of untreated periodontal disease periodontal treatment was offered. Increased bleeding may occur at home after patients had already left the clinic. Thus, only subjects with VWD were asked to

[name] & [name] (143/15: Version 2: 27.05.2015)

report any bleeding complications after periodontal probing and professional tooth cleaning.

# 5.7 Statistical analysis

The individual patient was used as statistical unit. All analyses were performed on patient level. BOP was defined as the main outcome variable and GBI as secondary outcome variable. All other parameters were control variables.

For all individuals, cigarette pack years were calculated. Group frequencies (VWD, control) were expressed for sex, current smoking. Group means and standard deviations were calculated for GBI, BOP, age, number of remaining teeth, pack years, CO, PCR, Body weight, VWF:Ag, VWF:RCO, FVIII:C, Hb1c. Further, for each individual the following variables were calculated to describe the periodontal status:

- Mean±standard deviation of PPD and PAL-V
- Percentage of PPD < 4 mm, 4 to 6.8 mm, ≥ 7 mm
- Sum of all PPD (Wohlfeil et al. 2009), i.e. the sum the PPD measured at all sites within a patient
- Sum of all PPD with BOP (Wohlfeil et al. 2009), i.e. the sum the PPD measured at all sites exhibiting BOP within a patient
- Periodontal inflamed surface area (PISA) [20, 21]. For each patient PPD were entered into an Excel sheet that can be downloaded freely (http://www.parsprototo.info/pisa.html).

From these group means and standard deviations were calculated. Comparisons between groups for dichotomous parameters were made by  $\chi^2$  or Fisher's exact test and for all other parameters by Mann-Whitney-U test. A post-hoc analysis was performed to estimate the test power that would be required to find a clinically relevant inter-group difference ( $\delta$ ) of 5.5% for BOP and GBI index with a type 1 error ( $\alpha$ ) of 0.05 for the actual sample size.

Using stepwise linear backward multiple regression analysis, factors should be identified that influenced BOP and GBI. The following independent variables were entered into the model for BOP: group (VWD/control), VWD type 2 or 3, sex, age, body weight, HbA1c, PCR, CO, aMMP-8, number of remaining teeth, PISA. The following independent variables were entered into the model for GBI: group (VWD/control), VWD type 2 or 3, sex, age, body weight, HbA1c, PCR, CO, aMMP-8, number of remaining teeth, PISA. Due to the fact that mean PPD is mathematically coupled to sum of PPD, sum of PPD with BOP, and PISA these 4 variables were not entered into the regression model at the same time. PISA provides the best representation of the subgingival inflamed area. Thus, PISA was chosen for the final model. The following parameters were described by dummy variables: group (control = 0, VWD = 1), sex (male = 0, female = 1), smoking status (never and former smoker = 0, current smoker = 1). All factors with p < 0.05 were kept in the models. For statistical analysis a PC program was used (SystatTM for Windows Version 13, Systat Inc., Evanston, USA).

[name] & [name] (143/15: Version 2: 27.05.2015)

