# 2. Background

## 2.1 Introduction and state of research

Von Willebrand Disease (VWD) is the most common inherent bleeding disorder [1]. The disease is caused by deficiency or dysfunction of von Willebrand factor (VWF), a plasma protein that mediates platelet hemostatic function and stabilizes blood coagulation factor VIII. VWF is also the carrier of factor VIII in plasma. Thus, its deficiency may also result in low levels of factor VIII.

Estimates for prevalence of VWD range between 0.6 and 1.3% [2]. Inherent VWD is classified into three main types (1, 2 and 3) with type 2 divided into four subtypes (A, B, M, N) [3]. The most prevalent and mildest form is VWD type 1 (about 75%) representing a partial quantitative deficiency of VWF [1]. VWD type 2 (qualitative defects of VWF) accounts for around 20 to 25% of cases [1]. Subtype 2A exhibits impaired VWF multimer assembly (group 1 mutations) or increased proteolysis of VWF in circulation (group 2 mutations). Subtype 2B shows increased, type 2M decreased affinity of VWF for platelet GPIb receptor. Subtype 2N is characterized by decreased factor VIII because of VWF deficiently binding to factor VIII [1]. VWD type 3 (0.6 to 6% of cases) represents complete quantitative deficiency of VWF [1, 3, 4]. These three major types of VWD may affect both males and females. Type 1 and type 2A and 2B are inherited in an autosomal dominant manner while type 2M, 2N and 3 are inherited in an autosomal recessive manner [3].

People with VWD bruise easily, have recurrent mucocutaneous bleeding, or bleed after tooth extraction, tonsillectomy or other surgery [5]. A common symptom of VWD is epistaxis (nose bleeding). Furthermore, women can have increased menstrual bleeding. Also a frequently reported symptom of VWD is gingival bleeding [6-8].

Gingival bleeding is also a leading symptom of plaque-induced gingivitis and untreated periodontal disease [4, 9, 10]. Interestingly case reports on VWD reporting spontaneous gingival bleeding as symptom did not look into periodontal health in detail. Abbas & Prabhu report "fair oral hygiene" and the gingival tissues to "look otherwise healthy" [6]. In another case continual bleeding 12 hours after scaling and polishing of the lower teeth is reported [8]. However, plaque indices or periodontal

[name] & [name] (143/15: Version 2: 27.05.2015)

variables as probing pocket depths (PPD) and vertical probing attachment level (PAL-V) [6, 8].

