# 5.2 Controls

For each case (VWD) a respective hematologically healthy control was recruited from the gingivitis and periodontitis patients of the Department of Periodontology, Center for Dentistry and Oral Medicine (Carolinum), Johann Wolfgang Goethe-University Frankfurt/Main. Each control was matched to one of the respective cases for sex, age (±5 years), self-reported smoking status (current smoker/non-smoker), number of

[name] & [name] (143/15: Version 2: 27.05.2015)

remaining teeth (±2 teeth), and periodontal diagnosis (gingivitis, chronic or aggressive periodontitis).

Smoking may interfere with gingival bleeding [11, 12]. Thus, all participants were asked about current and past cigarette smoking habits. Patients who reported smoking or had quit smoking for less than five years were classified as smokers [13]. Additionally the amount of carbon monoxide (CO) in exhaled air was measured using a Smokerlyzer® (Bedfont Smokerlyzer EC50-Micro; Bedfont Scientific Ltd, Rochester, Great Britain).

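### Controls are individually matched to cases, but BOP and GBI are tested as if the two groups were independent, which may cost power

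*Combined protocol and SAP*

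**What the plan says.** All references are to the combined protocol and SAP.

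- **Design (5.2 Controls).** Matching is individual and 1:1: "For each case (VWD) a respective hematologically healthy control was recruited". The matching factors are sex, age within 5 years, smoking status, number of remaining teeth within 2, and periodontal diagnosis.
- **Sample size (5.3).** 31 cases and 31 controls were planned, for a 5.5-point difference in GBI or BOP at 80% power and α of 0.05. Recruitment ended at 24 cases, and 24 cases with 24 matched controls were analysed.
- **Group comparison (5.7).** Each person counts as a separate unit. Dichotomous variables are compared by chi-square or Fisher's exact "test and for all other parameters by Mann-Whitney-U test". BOP and GBI are percentages per patient, so they fall under Mann-Whitney. No signed-rank test, paired t test, McNemar test, pair term or mixed model appears.
- **Power (5.7).** "A post-hoc analysis was performed to estimate the test power" for a 5.5-point difference at the actual sample size.
- **Regression (5.7).** Backward selection starts from 11 listed predictors, which include sex, age, number of teeth, CO and PISA. The retention rule is: "All factors with p < 0.05 were kept in the models".

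**The concern.** Matching on factors that drive the outcome makes pair members resemble each other. The protocol itself links two of its matching factors to bleeding. On smoking: "Smoking may interfere with gingival bleeding". On periodontal disease: "Gingival bleeding is also a leading symptom of plaque-induced gingivitis and untreated periodontal disease". A positive within-pair correlation is therefore plausible, although its strength is not documented.

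If it is positive, an independent-groups test uses too large a standard error. The direction of the error matters here. The hypothesis in section 3.1 is that bleeding is not primarily due to VWD, so a non-significant group difference is likely to be read as support. A conservative test, in a study that reached 24 of 31 planned cases, makes that result more likely even if VWD does raise bleeding. Pairing would not turn a non-significant result into evidence of no difference; that is a separate issue.

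**Working it through.** **Inputs from the documents:** 31 per group planned, 24 pairs analysed, difference 5.5 points, power 80%, α 0.05 with sidedness not stated (5.3); Mann-Whitney for BOP and GBI (5.7).

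**Assumptions:** the SD and the within-pair correlation ρ are not given. The SD is back-solved from the plan's own sample size, and ρ is varied from 0 to 0.5.

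**Step 1: implied SD.** Without an SD the planned 62 can be neither confirmed nor refuted, only inverted. By normal approximation, SD = 5.5 × √(31/2) / (z_α + z_0.80):

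- two-sided: 21.65 / (1.960 + 0.842) = 7.73 (7.605 by noncentral t)
- one-sided: 21.65 / (1.645 + 0.842) = 8.71 (8.61 by noncentral t)

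**Step 2: standard error.** The independent-groups SE of a mean difference is SD × √(2/n). With pairs it is SD × √(2(1−ρ)/n). For SD 7.605 and n = 24, the first is 7.605 × √(2/24) = 2.20. At ρ = 0.3 the second is 2.20 × √0.7 = 1.84. In general the SE is overstated by 1/√(1−ρ): 1.05, 1.12, 1.20 and 1.41 at ρ = 0.1, 0.2, 0.3 and 0.5.

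**Step 3: simulation.** 24 pairs, bivariate normal, 20,000 runs per setting, two-sided 5% tests, exact signed-rank (critical value 81). MW is Mann-Whitney and SR is signed-rank. The power columns are for a 5.5-point difference. The SD 8.7 column covers the case where planning was one-sided but testing is two-sided.

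| ρ | True type I error of MW, SD 7.605 | Power MW v SR, SD 7.605 | Power MW v SR, SD 8.7 |
|---|---|---|---|
| 0 | 5.0% | 66 v 65% | 55 v 54% |
| 0.1 | 3.8% | 67 v 69% | 55 v 58% |
| 0.2 | 3.1% | 67 v 74% | 55 v 62% |
| 0.3 | 2.1% | 69 v 80% | 56 v 69% |
| 0.5 | 0.8% | 72 v 91% | 57 v 83% |

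The type I error of signed-rank stays at about 5% throughout.

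**Step 4: skewed, bounded outcome.** Beta margins, SD 7.6, 10,000 runs. The control means of 12% and 20% are assumptions with no source in the documents.

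| ρ | MW v SR, control mean 12% | MW v SR, control mean 20% |
|---|---|---|
| 0 | 74 v 68% | 68 v 66% |
| 0.1 | 75 v 73% | 69 v 70% |
| 0.2 | 76 v 77% | 70 v 76% |
| 0.3 | 78 v 82% | 72 v 81% |
| 0.5 | 81 v 92% | 74 v 91% |

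A repeat of steps 3 and 4 with a different random seed agreed to within 1.5 percentage points.

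**Step 5: when do 24 pairs regain 80% power?** A paired t test needs an SD of the differences of at most 9.21 (noncentrality 5.5 / (9.21/√24) = 2.93, 23 df). Since SD of differences = SD × √(2(1−ρ)), this means ρ = 1 − (9.21/7.605)²/2 = 0.27, or 1 − (9.21/8.7)²/2 = 0.44.

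**Step 6: does the regression make up for it?** In part. Sex, age and number of teeth are entered, and CO and PISA stand in for smoking and disease burden. Periodontal diagnosis is in neither predictor list. Smoking status is given a dummy code but is also in neither list, so whether it was used is unclear. Backward selection may drop any of these terms, there is no pair term, and the Mann-Whitney comparison is unadjusted.

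**The case against.** The strongest reply is that the harm depends on a correlation nobody has reported. Matching on diagnosis uses broad classes (gingivitis, chronic or aggressive periodontitis), whereas section 5.6 separates four grades of chronic periodontitis. Plaque (PCR), a control variable, is not matched at all. The protocol's remarks on smoking and periodontal disease give a direction, not a strength. At low correlation the signed-rank test gains little, and with a skewed outcome it can be worse. Type I error is protected in any case.

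All of this stands. The rows at 0.3 and 0.5 are illustrations, not expectations, and a loss of power has not been demonstrated. It limits the size of the point but does not remove it: the design creates pairs and the analysis discards them.

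Two narrower replies also have force. First, the post-hoc power is not a separate flaw. For Mann-Whitney, power moves only from 66% to 72% across ρ = 0 to 0.5, so a calculation from group SDs is somewhat pessimistic for that test. It is far off only for what a paired analysis could detect. Second, changing the primary test after the data have been analysed is itself post hoc, so both results need to be shown.

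**Conclusion.** The point holds. Individually matched data are analysed with independent-groups tests, and no paired method is planned for BOP, GBI or any other variable. If the within-pair correlation is positive, p-values are too large and power is lost relative to a paired test. False positives are not inflated.

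For a normal outcome with SD 7.6, the loss runs from none at ρ = 0 to 11 points at 0.3 (80 − 69) and 19 to 20 points at 0.5. Signed-rank power reaches 80% only from about ρ = 0.3 (SD 7.6) or about 0.45 (SD 8.7). With an assumed control mean of 12%, signed-rank is the weaker test below about ρ = 0.2. These figures rest on a back-solved SD, assumed correlations and assumed distribution shapes. The change should be made, but the point does not invalidate the study. Confidence in the size is medium at best until the observed correlation is reported.

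**What to change.** **Main change.** Compare BOP (primary) and GBI (secondary) by Wilcoxon signed-rank test on the 24 within-pair differences, and report the Hodges-Lehmann difference with its 95% CI. Keep Mann-Whitney as a sensitivity analysis, so that the test written in section 5.7 remains visible.

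**Reporting.** Give the observed within-pair correlation and the SD of the differences; these settle how much the issue matters. If post-hoc power is still reported, base it on that SD. A value of about 9.2 points or less corresponds to 80% power for 5.5 points (paired t approximation).

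**Secondary changes.** In the BOP and GBI regressions, allow for the pairs with pair-clustered standard errors and a small-sample correction, or with a random pair intercept if it can be estimated. This does not stop backward selection from dropping matching terms. State whether smoking status was entered. Use exact McNemar for unmatched dichotomous variables such as aMMP-8. For sex and smoking, which were matched, describe the match instead of testing it.

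**Cost.** No new data are needed, provided the record of who was matched to whom was kept. Section 5.3 already describes the analysis as done, so this is a re-analysis to be disclosed as such. If the true correlation is zero, the price is about 1 point of power for a normal outcome and 3 to 6 points for a skewed one.

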#### **Control variables:**

- PCR (Plaque Control Record) (O'Leary 1972)
- Probing pocket depths (PPD)

[name] & [name] (143/15: Version 2: 27.05.2015)

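### No planned analysis guarantees a plaque-adjusted VWD effect on BOP or GBI

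*Combined protocol and SAP*

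**What the plan says.** - **Role of plaque.** Section 4 lists "PCR (Plaque Control Record") under control variables, together with probing depth. Section 5.7 adds that "BOP was defined as the main outcome variable and GBI as secondary outcome variable" and treats everything else as a control variable.
- **Matching.** Section 5.2: "Each control was matched to one of the respective cases for sex, age (±5 years), self-reported smoking status". Tooth count and periodontal diagnosis complete the list; plaque is not on it.
- **Group comparison.** In section 5.7, dichotomous parameters are tested by chi-squared or Fisher's exact test "and for all other parameters by Mann-Whitney-U test". BOP, GBI and PCR itself all fall under that clause. No covariate enters.
- **Regression.** Section 5.7 also plans backward stepwise linear models for BOP and for GBI, meant to find influencing factors. Each starts from 11 candidates: group, VWD type, sex, age, body weight, HbA1c, PCR, CO, aMMP-8, tooth count and PISA. The retention rule is "All factors with p < 0.05 were kept in the models".
- **Ranking.** Neither analysis is named as the one that decides the hypothesis in section 3.1.

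**The concern.** The study asks whether gingival bleeding in type 2 and 3 VWD comes from the coagulation defect or from inflammatory periodontal disease, and plaque drives the second explanation. Matching on diagnosis does not fix plaque: section 5.6 defines the diagnoses by probing depth and attachment level only, so two people with the same label can carry different amounts. Cases come from a haemophilia centre and controls from a periodontology department, so equal plaque cannot be presumed.

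The unadjusted comparison mixes any VWD effect with any plaque difference. The regression can separate them, but only if both terms survive selection. If PCR drops out, the group coefficient is no longer adjusted for plaque; if group drops out, there is no VWD estimate or interval. Even in the full model, group sits beside VWD type, so its coefficient is not a single overall VWD effect.

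Masking matters most here. A non-significant group difference would be read in favour of the study hypothesis, and lower plaque in cases could produce one despite a real VWD effect.

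**Working it through.** **Inputs from the documents.** Section 5.3: 31 + 31 "to detect an inter-group difference of 5.5% [4] GBI or BOP", "and a test power of 80" per cent, alpha 0.05, and 24 + 24 analysed. Section 5.7 plans a post-hoc power calculation for the same 5.5 points at an alpha "of 0.05 for the actual sample size".

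**Not in the documents.** The SD, the within-group PCR-BOP correlation r, and any PCR gap between groups. All three are assumptions below. The test is taken as two-sided, which is also not stated.

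**Step 1: the plan's sample size.** Without an SD, 31 per group cannot be reproduced independently; it can only be solved backwards. With the noncentral t, an SD of 7.6 gives 80% power at 31 per group. The normal approximation gives 5.5 × √(31/2) / (1.960 + 0.842) = 7.73. I use 7.6.

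**Step 2: unadjusted power at 24 + 24.** SE = 7.6 × √(2/24) = 2.19 and 5.5/2.19 = 2.51, so power is 69% by t test. Simulated Mann-Whitney power is 64-65%.

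**Step 3: effect of a plaque gap.** Shift in the unadjusted BOP difference = r × 7.6 × gap (in SDs of PCR). The false-positive rate and masked power follow from a t test with true difference equal to the shift, or to 5.5 minus the shift.

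| PCR gap (SD) | r | Shift (points) | Share of 5.5 | False-positive rate | Power if 5.5 is masked |
|---|---|---|---|---|---|
| 0.1 | 0.3 | 0.23 | 4% | 5.1% | 65% |
| 0.1 | 0.5 | 0.38 | 7% | 5.3% | 63% |
| 0.25 | 0.3 | 0.57 | 10% | 5.7% | 59% |
| 0.25 | 0.5 | 0.95 | 17% | 7.1% | 53% |
| 0.5 | 0.3 | 1.14 | 21% | 8.0% | 49% |
| 0.5 | 0.5 | 1.90 | 35% | 13.6% | 36% |

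A simulation with normal data (SD 7.73, 4000 runs per setting) at a gap of 0.5 SD agrees. Mann-Whitney false positives were about 7.5% (r = 0.3) and 12-13% (r = 0.5), with masked power of 45% and 33%. The PCR-adjusted linear model held about 5% false positives, with power of 67% and 76% under the same masking gap.

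**Step 4: precision with balanced groups.** Residual SD = 7.6 × √(1 − r²).

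| r | Residual SD | Power for 5.5 points at 24 + 24 |
|---|---|---|
| 0 | 7.60 | 69% |
| 0.2 | 7.45 | 71% |
| 0.3 | 7.25 | 73% |
| 0.5 | 6.58 | 81% |

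Stopping at 24 pairs cost 80 − 69 = 11 points of power. Adjustment returns 2, 4 or 12 of these at r = 0.2, 0.3 or 0.5.

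**Step 5: does selection keep both terms?** I simulated the stated backward rule with a true 5.5-point effect, PCR 0.5 SD lower in cases, 6 of 24 cases of type 3 (assumed) and eight unrelated covariates. Group and PCR both survived in about 41% of runs at r = 0.3 and 73% at r = 0.5.

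**The case against.** **PCR is in the plan.** A reader might infer that plaque is ignored, or that the Mann-Whitney test is the declared main analysis. The documents support neither. Group and PCR enter the BOP and GBI regressions together, and BOP is called the main outcome without any test being called the main analysis. That the two-group comparison decides the hypothesis is only an inference from the sample-size and power wording. What stands is narrower: the plan leaves the deciding analysis open, and the one that uses PCR may discard it or group.

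**Selection does least harm where the bias is largest.** In a simple model with group and PCR only, PCR is kept in about 95% of simulated studies at r = 0.5, 56% at r = 0.3 and 26% at r = 0.2. This is fair, and it tempers the 13.6% and 36% figures as a forecast for the regression; they describe the unadjusted test. But the planned model has 11 candidates, including PISA, which may displace PCR, and group can be dropped as well.

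**The gap is hypothetical.** No section says that cases and controls differ in plaque, or in which direction. If imbalance arises only by chance, the Mann-Whitney false-positive rate stays near 5%, and a gap of 0.5 SD or more occurs in about 8% of studies (0.5/√(2/24) = 1.73, two-sided). This stands, and is why the gap is shown as a range. The different sources of cases and controls make a systematic gap possible; they do not establish one.

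**An imbalance would be visible.** PCR is summarised and tested by group, and matching on diagnosis may narrow plaque differences. Both are partial safeguards. Showing an imbalance is not the same as removing its effect.

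**Conclusion.** The point holds: neither BOP nor GBI is assured a plaque-adjusted VWD effect with an interval. This follows from the text and needs no assumption.

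The size does rest on assumptions: SD 7.6, r of 0.3-0.5, and a systematic gap. The distortion is negligible at 0.1 SD, modest at 0.25 SD and material at 0.5 SD, where up to about a third of the 5.5-point target could be created or hidden. The one-sided reading of alpha implies an SD of about 8.7 and unadjusted power of about 71% at 24 per group, which does not change the conclusion.

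A reader might also infer that adjustment would make good the shortfall from stopping at 24 pairs. That is true only near r = 0.5, and the documents give no r. Control of bias is the stronger reason to adjust. This is a cheap improvement that should be made; it does not show that the study's result is wrong.

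**What to change.** In section 5.7, name one main BOP analysis: a linear model with group and PCR both forced in and no selection. The matched form is to regress the within-pair BOP difference on the within-pair PCR difference and read the intercept as the VWD effect. Report the adjusted difference with its 95% CI, and do the same for GBI. Keep the unadjusted comparison beside it, and label the stepwise model exploratory. Section 5.3 already reports the end of recruitment, so if the model is added after the data were seen, say so.

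The cost is one degree of freedom, a linearity assumption and a little analysis of data already recorded at six sites per tooth. One point of interpretation remains: if VWD itself changes brushing, the adjusted figure is the effect beyond plaque, which is why both figures should be shown.

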## 3. Aim

#### 3.1 Hypothesis

The sypmtome gingival bleeding in patients suffering from VWD type 2 and 3 is not primarily due to VWD but due to inflammatory periodontal diseases (gingivitis, periodontitis).

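### Section 5.7 plans no matched confidence interval for the VWD-minus-control difference in BOP or GBI, so a null result cannot show whether 5.5 points is excluded

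*Combined protocol and SAP*

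**What the plan says.** The hypothesis in Section 3.1 is that gingival bleeding in type 2 and 3 VWD "is not primarily due to VWD but due to inflammatory periodontal diseases (gingivitis, periodontitis"). Controls are individually matched (Section 5.2): "Each control was matched to one of the respective cases for sex", age, smoking status, number of teeth and periodontal diagnosis.

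Section 5.3 says that 31 cases and 31 controls "was required to detect an inter-group difference of 5.5"% in GBI or BOP, with alpha 0.05 and 80% power. Recruitment ended early: "Thus, the study was analyses with 24 cases and 24 matched controls".

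For the group comparison, Section 5.7 plans four outputs:

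- Descriptive: "Group means and standard deviations were calculated for GBI, BOP, age" and other variables.
- Tests: chi-squared or Fisher's exact test for dichotomous variables, "and for all other parameters by Mann-Whitney-U test".
- Power: "A post-hoc analysis was performed to estimate the test power that would be required to find a clinically relevant inter-group difference" of 5.5% at the sample size reached.
- Regression: backward elimination from a list that includes both group and VWD type, under the rule "All factors with p < 0.05 were kept in the models".

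The available text contains no confidence interval for the difference, no within-pair difference, no exclusion margin and no rule for reading a null result.

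**The concern.** On the VWD part of the hypothesis, finding no group difference is the favourable result. A p-value above 0.05 says only that zero is compatible with the data. The plan itself calls 5.5 points clinically relevant, so the reader needs to know whether 5.5 is also compatible.

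The planned power figure does not answer this. Power for a fixed 5.5 points depends on the SD, n and alpha. It is the same whether the observed excess is 0 or 4 points. The shortfall from 31 to 24 cases makes an inconclusive null result a real prospect.

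Planned means and SDs let a reader build an approximate unpaired interval. They do not allow one that respects the matching, because group summaries lose the pairing.

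**Working it through.** **Inputs.** From Section 5.3: difference 5.5 (read as percentage points), alpha 0.05, power 80%, 31 per group planned, 24 per group reached. Not given: SD, sidedness, within-pair correlation r. A t-based calculation stands in for the Mann-Whitney test.

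**1. The plan's own figure.** Without an SD, 31 per group cannot be reproduced, so the SD is solved for.

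- Two-sided normal approximation: SD = 5.5 × √(31/2) / (1.960 + 0.842) = 21.65 / 2.802 = 7.73.
- Two-sided noncentral t, 60 df: SD = 7.60, used below.
- One-sided noncentral t: SD = 8.61.

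**2. Power at 24 + 24.** The noncentrality is 5.5 / (SD × √(2/24)), with 46 df. At SD 7.6 it is 5.5 / 2.195 = 2.51, and power is 0.689. At SD 6 power is 0.875; at SD 10 it is 0.462. The one-sided reading (SD 8.61) gives 0.704.

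**3. Unpaired 95% half-width.** This is t(0.975, 46) × SD × √(2/24), with t = 2.013.

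| SD | Half-width h | Observed excess that is non-significant yet does not exclude 5.5 (5.5 − h to h) |
|---|---|---|
| 6 | 3.49 | 2.0 to 3.5 |
| 7.6 | 4.42 | 1.1 to 4.4 |
| 10 | 5.81 | −0.3 to 5.8 |

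At SD 10, even an observed difference of zero would leave 5.5 inside the interval.

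**4. Paired 95% half-width.** This is t(0.975, 23) × SD × √(2(1 − r)/24), with t = 2.069 and SD 7.6.

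| r | Half-width h | Band 5.5 − h to h |
|---|---|---|
| 0 | 4.54 | 1.0 to 4.5 |
| 0.3 | 3.80 | 1.7 to 3.8 |
| 0.5 | 3.21 | 2.3 to 3.2 |

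The band is empty once h < 5.5/2 = 2.75. At SD 7.6 that needs r > 1 − (2.75/4.54)² = 0.63. The threshold is 0.41 at SD 6 and 0.79 at SD 10.

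**5. How often a null result would be ambiguous.** This was simulated with normal data, SD 7.6 and the planned Mann-Whitney test. The test is non-significant while the upper limit of the paired Hodges-Lehmann interval is still at least 5.5 in 33%, 19% or 9% of trials with no true difference (r = 0, 0.3, 0.5). With a true 4-point excess the figures are 50%, 49% and 47%.

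**The case against.** The strongest reply is that this is a reporting gap. Means and SDs are planned, so an unpaired interval is one line of arithmetic away. Power is calculated at a fixed 5.5 points and not at the observed difference, so the plan already considers how informative a null result would be. The regression also looks for positive evidence of inflammatory factors, so the hypothesis does not rest on the null result alone. Every figure above depends on an SD and a correlation that the documents do not give.

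All of this stands, and it limits the point to the VWD part of the hypothesis. It does not supply an interval that uses the pairing, nor tell a reader whether 5.5 is excluded.

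Three stronger readings are tempting and not supported:

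- *The plan treats non-significance as proof.* It does not say so; it gives no rule either way.
- *The plan ignores its own margin.* The documents set 5.5 as a difference to detect and call it clinically relevant. They never set it as a margin to exclude.
- *Group leaving the backward regression is a null VWD result.* The candidate list also holds a VWD type term, which carries group information because only cases have a type. Its coding is not given. In a simulation with a true 5.5-point effect, SD 7.6, an assumed 0/2/3 coding, six type 3 cases and no prognostic covariate, group was dropped in about 55% of trials, but both VWD terms in only about 28%. No elimination rate is therefore offered here as the size of the problem.

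**Conclusion.** The point holds as a gap in the planned outputs, and it should be fixed. The planned tests are not made invalid. What they cannot do is show whether a VWD excess of 5.5 points is ruled out, and the only interval a reader could derive ignores the matching.

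The absence of an interval does not depend on any assumption. Its consequence does. The central figures (power 69%, unpaired band 1.1 to 4.4 points) rest on an SD of 7.6 inferred from 31 per group, two-sided testing and approximately normal data. The paired band also depends on r, and a correlation above about 0.63 would remove it at that SD. Excluding 5.5 points would still not settle whether bleeding is primarily inflammatory, since the plan does not define that word as a number.

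**What to change.** In Section 5.7, keep the power sentence as the record of an analysis done, and add:

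> The VWD-minus-control difference in BOP (primary) and GBI (secondary) is reported with a two-sided 95% CI from the 24 matched pairs (paired Hodges-Lehmann). Absence of a relevant excess is concluded for BOP only if the upper limit for BOP is below 5.5 percentage points (one-sided 2.5%); otherwise the result is inconclusive on this point. The GBI interval is supportive.

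State that 5.5 was set as the difference to detect, that using it as an exclusion margin is post hoc if adopted after the data were seen, and that the rule does not by itself settle the causal hypothesis.

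For each outcome, also report the group coefficient with its 95% CI from one fixed model without p-value elimination:

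- Group is kept whatever its p-value, and VWD type is left out so that all cases are compared with controls.
- Covariates are the matching factors, PCR and HbA1c.
- Smoking status and periodontal diagnosis are taken as defined for matching in Section 5.2. Section 5.7 codes all former smokers as non-smokers, whereas Section 5.2 counts those who quit less than five years ago as smokers. Section 5.6 lists five diagnostic classes, none of them aggressive periodontitis.
- PISA is left out unless it is computed without BOP; otherwise the outcome would help to predict itself.

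In Section 5.3, give the SD and sidedness used and the resulting power at 24 + 24.

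The cost is wording, one interval and one extra model per outcome, all from data already collected. If matching induces no correlation, the paired t interval is slightly wider than the unpaired one (4.5 against 4.4). Absence of a relevant excess will also be concluded less often than non-significance. With no true difference, SD 7.6 and normal data, the rule is met in 65%, 80% or 91% of trials at r = 0, 0.3 or 0.5, against 95% to 99% non-significant by Mann-Whitney.
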